#### **11.8.2 Causality of an Adverse Event**

The PI will use the following question when assessing causality of an AE to the study product/intervention: *Is there a reasonable possibility that the study product/intervention caused the event?*

“Reasonable possibility” means that there is evidence to suggest a causal relationship between the study product/intervention and the AE. This does NOT mean that the relationship cannot be ruled out. Examples of types of evidence that would suggest a causal relationship between the study product and AE are the following:

- A single occurrence of an event that is uncommon and known to be strongly associated with study product exposure (e.g., angioedema, hepatic injury, Stevens-Johnson syndrome).
- One or more occurrences of an event that is not commonly associated with study product exposure but is otherwise uncommon in the population exposed to the study product (e.g., tendon rupture).

The PI will use clinical judgment to determine if he or she believes there is a reasonable possibility of a causal relationship with the study product. Using merely the temporal sequence to determine causality is not sufficient. Rather, known or presumed pharmacologic or biologic action of the study product or class of study products should be considered in the assessment. Dose-response relationship, prior similar AE(s) with similar or identical study product(s), improvement following study product discontinuation, and recurrence upon re-challenge are among the most robust supportive evidence for a causal

relationship. Alternative etiologies, such as natural history of underlying diseases, new disease/disorder development, concomitant therapy, and other risk factors, will be considered and investigated. The PI will also consult the IB or other study product information for his/her assessment.

An affirmative answer designates the event as a Suspected Adverse Reaction (SAR).

The following information will be reported for each event and must be reviewed by the PI or designee: 1) description of the event, 2) start date, 3) stop date, 4) severity of the event, 5) causal relationship to study product/intervention, 6) seriousness, 7) outcome of the event, and 8) if action with study product/intervention was required.

### **11.8.3 Reporting Requirements**

#### **11.8.3.1 Adverse Event Reporting**

Regardless of severity or relationship to the study product, all AEs occurring after informed consent and through the Month 36 study visit must be recorded in the subject's eCRF. The following information and assessments should be recorded in the AE section of the eCRF:

- The date of onset of the event and date it ended.
- The signs, symptoms, or diagnosis of the event.
- The AE severity using the criteria outlined above.
- The relationship of the event to the study drug.
- The seriousness of the event according to definitions outlined above.
- A description of any action taken regarding study drug disposition.
- Any additional data which might be relevant to the event.

All adverse events, regardless of the PI's determination as related or unrelated to the investigational product, are to be reported in the Advantage eClinical. AEs will be reviewed on a weekly basis by the medical monitor or his/her designee and cumulative AE reports will be shared with the data safety monitoring board per the charter. All SAEs will be reviewed within one business day of notification.

#### **11.8.3.2 Serious Adverse Events Reporting**

SAEs are considered immediately reportable events.

Full details of the SAE event, treatment, and an assessment of the relationship to the study drug must be provided in the report. SAEs will be captured from time of informed consent through the Month 36 visit.

If a subject experiences an SAE, the PI must:

- Report the SAE by entering the data into the Advantage eClinical system immediately (within 24 hours) after the PI becomes aware of the event. If Advantage eClinical is not available, the site should report the SAE via email at [tol\\[contact]](mailto:[contact]).
- Obtain and maintain all pertinent medical records, information, and medical judgments of medical personnel who assisted in subject's treatment and follow-up and document on CRF as appropriate.
- Provide a more detailed report to both Emmes (via Advantage eClinical) and the IRB/IEC no later than seven days after the PI discovers the event as further information becomes available, and, when necessary, update the information with follow-up information, including outcomes. This report should include a statement on whether the event considered related to the use of investigational product by the PI.
- The PI will notify the IRB/IEC of the SAE according to specific IRB/IEC requirements.

The following attributes must be provided by the PI or designee immediately on being notified of a serious event:

- Description of event, diagnosis when applicable
- Date of onset and resolution (if known when reported)
- PI/designee assignment of severity
- PI/designee assessment of causality to the study product/intervention
- Action taken with study product/intervention (e.g., stoppage)

After the SAE has been reported by the PI and assessed by the Medical Monitor and the Sponsor, they must report the event to the appropriate regulatory authorities using one of two options:

- Standard reporting (report in the annual report). This option applies if the AE is classified as one of the following:
  1. Serious, expected, suspected adverse reaction (serious, expected, and related)
  2. Serious and not suspected adverse reaction (serious and not related)
- Expedited reporting. This option is required if the AE is classified as serious and unexpected, suspected adverse reaction (serious, unexpected, and related).

The Sponsor must report an AE as a suspected adverse reaction (related AE) only if there is evidence to suggest a causal relationship between the study drug and the AE, such as:

- A single occurrence of an event that is uncommon and known to be strongly associated with study drug.
- One or more occurrences of an event that is not commonly associated with the study drug but is otherwise uncommon in the population exposed to the study drug.
- Aggregate analysis of specific AEs and SAEs observed in a clinical trial (such as known consequences of the underlying disease or condition under investigation or other events that commonly occur in the study population independent of the study drug) that indicates those events occur more frequently in the study drug group than in a concurrent or historical control group.
- Any findings from clinical or epidemiological studies, analysis of data pooled across multiple studies, published or unpublished scientific papers, or from animal or *in vitro* testing that would result in a safety-related change in the protocol, informed consent, or other aspects of the overall conduct of the trial.

The Sponsor will be responsible for notifying the Food and Drug Administration (FDA) of any unexpected fatal or life-threatening suspected adverse reaction as soon as possible, but in no case later than 7 calendar days after the Sponsor's initial receipt of the information. In addition, the Sponsor must notify FDA and all participating PIs in an Investigational New Drug (IND) safety report of potential serious risks, from clinical trials or any other source, as soon as possible, but in no case later than 15 calendar days after the initial receipt of the information regarding any AE associated with the use of the investigational product that is both serious and unexpected.

All SAEs will also be reported quarterly to the DSMB.

The PI will collect information on SAEs until the subject's health has returned to baseline status, all parameters have returned to normal, or remaining health issues have otherwise been explained.

### **11.8.3.3 Collection and Follow-up of AEs and SAEs**

Qualified research staff will elicit subject reporting of AEs, including SAEs, from the time the subject signs informed consent. The research staff will obtain as much information as possible about the reportable AE/SAE to complete the AE/SAE CRF(s) and will consult with the PI as warranted. The information will be reviewed by the PI and assessed for seriousness, severity, and causal relationship. Appropriate site staff will review all AE documentation and verify accuracy of assessments to ensure that all AEs are appropriately reported and to identify any unreported AEs that require reporting. Each participating site's

PI is responsible for study oversight, including ensuring human research subject protection by designating appropriately qualified, trained research staff and assessing, reporting, and monitoring AEs.

CRA's will visit the study sites and review the study data on a regular basis. They will also promptly advise sites to report any previously unreported AEs and ensure that the AEs are being followed appropriately by the research staff. The CRA will ensure that any unreported or unidentified SAEs discovered during visits are promptly reported by the site. Staff education, re-training, or appropriate corrective action plan will be implemented at the participating site when unreported or unidentified AEs are discovered, to ensure future identification and timely reporting by the site. The study Medical Monitor or his/her designee will review all reported AEs/SAEs throughout the study. Multiple safety monitoring layers will be provided by:

- All SAEs reported will undergo Medical Monitor review within one business day of notification of the SAE
- Weekly review of all reported AEs using listings generated from the data system; the review will entail both what was reported in the preceding week and cumulatively from study inception for trends and safety signals
- MedDRA coding of all AEs will be performed on a quarterly basis to ensure consistency of terminology; the coding process will also entail review for trends and safety signals
- Document preparation for periodic DSMB meetings; cumulative safety data will be reviewed for trends and safety signals at the time of document preparation and review

The study DSMB will also review safety data for this trial periodically at regularly scheduled meetings.

AEs, including SAEs, will be reported to the central IRB according to central IRB requirements. This will be reviewed on site by the CRA for the study.

All SAEs as defined earlier will be reported to the PI, Medical Monitor or his/her designee, and the Sponsor.

#### **11.8.3.4 Pregnancy**

Pregnancy is not considered an AE, but any pregnancies that occur during the study will be tracked on a pregnancy case report form. Pregnancy is an exclusion criterion. If a study subject was pregnant on the day of study product administration (e.g., due to a false negative pregnancy test) or becomes pregnant afterwards, the subject will be followed through the end of her pregnancy. The subject will not receive any additional doses of

study medication but would be encouraged to continue to attend the remaining study visits. If the subject is unwilling to do so, she should be asked to return to the study center to complete the assessments specified in the End-of-Study Visit (Week 52). Any complications of pregnancy or termination of pregnancy due to medical reasons will be considered a SAE as defined in Section 11.1. The PI should be informed immediately of any pregnancy, and all available pregnancy information should be entered into Advantage eClinical within 24 hours of becoming aware of the event. The PI should counsel the subject and discuss the risks of continuing with the pregnancy and the possible effects on the fetus. The site will be asked to follow-up with the subject periodically during the pregnancy for ongoing health and safety information through the conclusion of the pregnancy. Follow-up information detailing the outcome of the pregnancy should be entered into the Advantage eClinical system as it becomes available. If the pregnancy results in normal childbirth with a healthy, normal infant, no SAE will need to be reported. If the pregnancy results in a congenital anomaly/birth defect, an SAE must be reported following the SAE reporting procedures in the protocol. Any premature termination of the pregnancy will be reported.

### **11.9 Follow-Up of Adverse Events and Serious Adverse Events and Final Reports**

AEs, including SAEs, will be followed until resolved or resolved with sequelae, (i.e., medically stable). AEs ongoing at the time of the last visit will be marked as ongoing however SAEs will be followed through resolution or up to 30 days, whichever comes first. The site must actively seek information about an SAE as appropriate until the SAE is resolved or considered resolved with sequelae.

Non-serious AEs that are identified during the last scheduled study visit (Week 54 or early discontinuation) must be recorded on the AE CRF as ongoing.

Any clinically significant abnormal test results (e.g., laboratory findings) at the final assessment should be followed to resolution or until determined by the PI to be stabilized. Repeat tests may be indicated to establish this.

If a subject has any clinically significant, study-related abnormalities at the end of the study, the Medical Monitor should be notified, and every effort should be made by the PI to arrange follow up evaluations at appropriate intervals to document the course of the abnormalities.

All suspected serious adverse reactions regardless of expectedness must be followed until resolution or until the event is considered resolved with sequelae (i.e., medically stable, beyond the end of the study if needed). All other events that cannot be resolved within 30 days after last study contact (e.g., consent withdrawal, lost to follow-up) or after the last

study visit will be considered ongoing and entered into Advantage eClinical with that outcome.

SAEs that are identified on the last scheduled contact must be recorded on the AE CRF page and reported to Emmes according to the reporting procedures outlined in Section 11.8.3 and the Safety Monitoring Plan (SMP). This may include unresolved previously reported SAEs, or new SAEs. The PI should follow these SAEs until the events are resolved, or the subject is lost to follow-up. The PI should continue to report any significant follow-up information to the Medical Monitor and the IRB up to the point where the event has been resolved. Resolution means the subject has returned to the baseline state of health, or the PI does not expect any further improvement or worsening of the subject's condition.

Any new SAEs reported by the subject to the PI that occur after the last scheduled contact and are determined by the PI to be reasonably associated with the investigational product should be reported in Advantage eClinical and to the IRB.

**Table 5: Adverse Event Status and Outcomes**

Status	Definition
Recovered/ Resolved	One of the possible results of an adverse event outcome that indicates that the event has improved or recuperated.
Recovered/ Resolved with sequelae	One of the possible results of an adverse event outcome that indicates the subject recuperated but retained pathological conditions resulting from the prior disease or injury.
Recovering/ Resolving	One of the possible results of an adverse event outcome that indicates that the event is improving.
Not Recovered/ Not Resolved	One of the possible results of an adverse event outcome that indicates that the event has not improved or recuperated.
Fatal	The termination of life as a result of an adverse event.

## **12 DATA MANAGEMENT AND PROCEDURES**

### **12.1 Design and Development**

This protocol will utilize Emmes, a CRO selected by the Sponsor. Emmes will be responsible for developing the CRFs, developing and validating the clinical study database, ensuring data integrity, and training site staff on applicable data management procedures. A web-based distributed data entry model will be implemented. Advantage eClinical will be developed to ensure that guidelines and regulations surrounding the use of computerized systems used in clinical trials are upheld. The remainder of this section provides an overview of the data management plan associated with this protocol.

### **12.2 Data Center Responsibilities**

Emmes will 1) develop and apply data management procedures to ensure the collection of accurate and good-quality data, 2) provide final CRFs and electronic CRFs (eCRFs) for the collection of all data required by the study, 3) develop data dictionaries for each CRF that will comprehensively define each data element, 4) prepare instructions on the use of Advantage eClinical and the completion of CRFs, 5) conduct ongoing data validation and cleaning activities on study data collected from all study sites; and 6) perform data validation and cleaning activities prior to any interim analyses and prior to the final study database lock.

### **12.3 Data Acquisition and Entry**

Data will be collected at the study sites on source documents and entered by site staff into eCRFs in Advantage eClinical. Emmes will provide the sites with paper CRF source documents and completion instructions. Data will be entered into Advantage eClinical by site staff according to the instructions provided during training and with the guidelines established by Emmes. Data entry into the eCRFs must be performed by authorized individuals.

Subject diary data will be captured electronically and incorporated into the study database for analysis. Laboratory data and CGM data will be entered into an electronic database and transferred to Emmes for inclusion in the study database.

The PI at each site is responsible for maintaining accurate, complete, and up-to-date research records. In addition, the PI is responsible for ensuring the timely completion of eCRFs for each research subject. The PI will be required to provide attestation for each subject that all information entered into Advantage eClinical is correct and accurate.

## **12.4 Data Validation and Editing**

Data will be entered on source document prior to entry in Advantage eClinical. Site staff are expected to follow ALCOA-C (Attributable, Legible, Contemporaneous, Original, Accurate, and Complete Data) principles when completing and editing source documents.

Emmes will monitor eCRFs for completeness and accuracy throughout the study. Dynamic reports listing missing values and forms are available to sites in Advantage eClinical. Emmes also will identify inconsistencies within eCRFs and between eCRFs and post-data clarification requests or queries in Advantage eClinical on a scheduled basis. Emmes will develop a Data Validation Plan detailing the procedures for data collection, edit checks, data queries and corrections, and data processing to provide a clean database for analysis. The Sponsor will approve the plan.

In addition, Emmes will conduct on-site monitoring visits, during which audits comparing source documents to the data entered on the eCRF will be performed. Any discrepancies identified between the source document and the eCRF will be corrected by the site. Sites will resolve data inconsistencies and errors by updating the appropriate source document as well as entering all corrections and changes into Advantage eClinical.

## **12.5 Data Transfer / Lock**

At the conclusion of data collection through 30 patients reaching Week 24, Week 24 and Week 54, Emmes will perform cleaning activities and will “freeze” the study database. A final data “lock” will be conducted upon completion of data collection for the follow-up safety visits through Month 36. Prior to the final lock, Emmes will perform final cleaning activities and the study database will be “locked” from further modification. SAEs will be captured from time of informed consent through the Month 36 visit. The final analysis datasets will be transferred to the Sponsor, as requested, for storage and archiving.

## **12.6 Data Training**

Emmes will train site staff on the assessments, eCRF completion guidelines, data management procedures, and the use of Advantage eClinical.

## **12.7 Data Quality Assurance**

To address the issue of data entry quality, Emmes will follow a standard data monitoring plan. An acceptable quality level prior to study lock or closeout will be established as a part of the data management plan. Data quality summaries will be made available during the protocol.

## 13 STATISTICAL CONSIDERATIONS

### 13.1 Sample Size/Power Considerations

Up to 99 subjects will be randomized 2:1 to active and placebo treatments. For analytic purposes all subjects 12- <41 years of age will be considered cohort A. A minimum of 18 and a maximum of 24 subjects aged 12 and <18 years of age will comprise Cohort B. Adult subjects aged 18- <41 will comprise cohort C. The proposed study is powered to detect approximately an overall 13% difference between treatment and placebo groups in a repeated measures mixed model analysis of the mean plasma C-peptide AUC over 4-hour MMTT at Week 12, 16, and 24 weeks as compared to the subject's baseline. A total of 90 subjects will provide 90% power to detect this difference at a significance level (alpha) of 0.05; a total of up to 99 subjects will be randomized to allow for an anticipated drop-out rate of approximately 10%. Insulin secretion as reflected by C-peptide declines more rapidly in younger patients, including adolescents. TOL-3021 is expected to have equal or even greater effect in the adolescent population compared to the effect observed in the phase 2a study of adult subjects only. An effect was detectable in the 17 adults who received 12 weeks of 1.0 mg treatment in that study. Based on assumption of an overall difference between treatment and placebo groups of 20%, then a minimum of 18 adolescents aged 12- <18 (Approximately 12 active and 6 placebo) would provide 80% power to detect a difference at a significance level (alpha) of 0.05, providing an initial estimate of efficacy and a description of safety in this population Cohort B (ages 12- <18) and cohort C (ages 18- <41) and will be analyzed separately as well as combined.

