**5 STUDY POPULATION****5.1 Number of Subjects**

Up to 99 subjects will be randomized in a 2:1 ratio of treatment with TOL-3021 to placebo with a minimum of 18 and a maximum of 24 subjects aged 12 and <18 years of age.

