### **13.3.3 Efficacy Analysis**

The analysis of the primary outcome, MMTT-stimulated 4-hour mean C-peptide AUC at multiple time points will test the null hypothesis of “no treatment group difference” versus the two-sided alternative using the intent-to-treat (ITT) cohorts. The treatment-group main effect hypothesis test will be derived from a repeated measures mixed model of the log-transformed 4-hour C-peptide AUC response at 12, 16 and 24 weeks, adjusted for the baseline C-peptide AUC, age group and T1D-duration group. Missing data for this analysis will be imputed for each subject based on any available data. To be imputed, a data point must have data for the visit before and the visit after the missing data point, and the slope between the two non-missing visits will be used to impute the missing data. A secondary method using a mixed model for repeated measures (MMRM) approach will also be utilized for the primary and secondary endpoints that cannot be imputed using the approach above. Additional details for this approach will be provided in the statistical analysis plan.

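### The 80% power claimed for Cohort B at the minimum of 18 adolescents omits the drop-out allowance used for the whole trial; at that minimum it is about 75%, if the 80% is right

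*Protocol*

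**What the plan says.** Section 13.1 contains two power statements.

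- **Whole trial.** 90 subjects give 90% power for a difference of about 13%, and "a total of up to 99 subjects will be randomized to allow for an anticipated drop-out rate of approximately 10" per cent. The number that carries the power and the number randomised are kept apart.
- **Cohort B (ages 12 to under 18).** "Based on assumption of an overall difference between treatment and placebo groups of 20" per cent, "then a minimum of 18 adolescents aged 12- <18 (Approximately 12 active and 6 placebo) would provide 80% power to detect a difference" at alpha 0.05. One number, 18, carries the power.

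That 18 is a count of randomised subjects. Section 5.1 sets the randomised total "with a minimum of 18 and a maximum of 24 subjects aged 12 and <18 years of age", and the sample-size entry of the synopsis says the same. No separate evaluable number and no drop-out rate is given for adolescents. Section 13.1 says Cohorts B and C will be analysed separately as well as combined. It describes the Cohort B result as an initial estimate of efficacy alongside a description of safety.

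**The concern.** The two statements follow different conventions. In the first, the randomised number is larger than the number needed, to absorb losses. In the second they are the same number, so 80% is reached at the minimum only if no adolescent is lost. With about six placebo subjects, each loss in that arm is costly. At a 10% loss per subject, the chance that all 18 complete is 0.9^18 = 15%, and the chance of losing at least one of six placebo subjects is 1 − 0.9^6 = 47%.

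At stake is the stated justification for the minimum of 18. A reader of section 13.1 would expect 80% power for the adolescent analysis from a trial that just meets its minimum, and the protocol's own drop-out rule does not support that.

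**Working it through.** **Inputs.** From section 13.1: Cohort B 12 versus 6, difference 20%, power 80%, alpha 0.05; whole trial 90 subjects at 2:1 (60 versus 30), difference 13%, power 90%; drop-out about 10%, stated for the whole trial. From section 13.3.3: a two-sided test ("versus the two-sided alternative using the intent-to-treat (ITT) cohorts"). No SD is stated anywhere.

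**Step 1: the plan's own figure.** Without an SD the 80% cannot be reproduced directly, so it is taken as given. Use a two-sided two-sample t test with noncentrality δ = d × √(n1·n2/(n1+n2)) and power = P(T′ > t_crit) on n1+n2−2 degrees of freedom. At 12 versus 6, √(72/18) = 2, t_crit = 2.120, and power is exactly 80% when d = 1.492 (δ = 2.985). A 20% difference then implies an SD of 0.20/1.492 = 0.134. Steps 2 and 3 use only d, so the missing SD does not affect them.

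**Step 2: apply the protocol's drop-out convention.** 18 × 0.9 = 16.2, or 10.8 versus 5.4.

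| Analysed (active v placebo) | √(n1·n2/(n1+n2)) | δ | Power |
|---|---|---|---|
| 12 v 6 (no loss) | 2.000 | 2.985 | 80.0% |
| 10.8 v 5.4 (10% loss) | 1.897 | 2.831 | 75.1% |
| 11 v 5 (one lost per arm) | 1.854 | 2.767 | 73.0% |
| 10 v 6 (two active lost) | 1.936 | 2.890 | 76.7% |
| 12 v 5 (one placebo lost) | 1.879 | 2.803 | 74.6% |
| 11.4 v 5.7 (drop-outs keep half their information) | 1.949 | 2.909 | 77.6% |

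Averaged over random 10% loss in each arm, power is 74.4%. A normal approximation gives 75.7% at 10.8 versus 5.4, so the choice of test matters little.

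**Step 3: how far up the permitted range the problem reaches.** 18/0.9 = 20. Twenty randomised at 2:1, less 10%, leaves 12 versus 6 and 80.0%. The maximum of 24, less 10%, leaves 14.4 versus 7.2 and 87.4%.

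**Step 4: the same rule on the whole trial.** 99 × 0.9 = 89.1 (59.4 versus 29.7). With d = 0.733, which gives 90% at 60 versus 30, power is 89.7%. The whole-trial claim holds under its own rule.

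**Step 5: is the 80% itself supported?** Solve for the SD that makes 60 versus 30 give 90% at 13%, and apply it to 12 versus 6 at 20%, two-sided t. The scale of the percentage is not stated, so three readings are shown.

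| Reading of 13% and 20% | Implied SD | d at 20% | Power at 12 v 6 |
|---|---|---|---|
| Raw | 0.13/0.733 = 0.177 | 1.127 | 56% |
| log(1.13), log(1.20) | 0.167 | 1.093 | 54% |
| −log(0.87), −log(0.80) | 0.190 | 1.174 | 60% |

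One-sided and normal-approximation variants extend the range up to 67%. None reaches 80%.

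**The case against.** The strongest reply is that 75% is not what the trial would deliver.

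- **The 10% is a whole-trial rate.** It has no adolescent counterpart and no stated time horizon. Dosing lasts 52 weeks, but the primary endpoint closes at Week 24. This stands: applying 10% to Cohort B is an assumption.
- **Drop-outs may still contribute.** The model uses Weeks 12, 16 and 24, and section 5.3.1 encourages subjects who stop study drug to remain in the study. Someone leaving after Week 12 has primary-outcome data. This also stands, and the half-information row shows its effect. But the step from 90 to 99 counts drop-outs as lost, so the 75% follows the protocol's own convention.
- **The 12 versus 6 split is only approximate.** Randomisation is stratified by diabetes duration, not age (section 6). With no drop-out at all, 13 versus 5 gives 75.9% and 11 versus 7 gives 82.6% on the same method. A chance shift of one subject is about as large as the drop-out effect.
- **The protocol can meet its claim as it stands.** Twenty or more adolescents is within the permitted range. True, but the 80% is attached to the minimum.

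A reader might infer that the minimum delivers 74% to 75% whatever else is true, or always misses the target by five points or more. The documents do not support that: two losses from the active arm cost 3.3 points, and retained data in the mixed model cost 2.4.

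**Conclusion.** The omission is real. Section 13.1 attaches 80% power to a randomised minimum without the allowance it makes for the whole trial. Conditional on 80% at 12 versus 6, a 10% adolescent drop-out and drop-outs counted as lost, power at the minimum is about 75% (73% to 77% by which arm loses subjects). It is about 78% if drop-outs keep half their information. Enrolling 20 or more removes the shortfall.

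It would be tempting to read 75% as the likely actual power. The documents do not support that either, because the figure inherits an 80% with no stated SD that the 90-subject sizing does not reproduce (about 54% to 60%). A different SD for adolescents could reconcile the two, but the protocol does not state one.

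Severity is minor. The primary analysis on all subjects is unaffected, and Cohort B is presented as an initial estimate of efficacy.

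**What to change.** 1. State the SD, and the scale of the 20% difference, behind the Cohort B figure, and confirm or correct the 80% before restating it.
2. In section 13.1, describe the resulting figure as power for 18 evaluable adolescents. Add that 18 randomised with 10% drop-out leaves about 16 and gives about 75%, conditional on the 80% input.
3. Optionally, set the Cohort B minimum at 20 (18/0.9) in the synopsis and in sections 5.1 and 13.1. This stays within the cap of 24 and the total of 99.

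Items 1 and 2 cost a sentence or two and a less favourable figure. Item 3 adds no subjects overall but may lengthen adolescent recruitment slightly. It restores 80% only if item 1 confirms that 12 versus 6 gives 80%.

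### The 80% power stated for 18 adolescents does not fit the 90% stated for 90 subjects: with a common SD, 12 v 6 has about 54–60% power for a 20% difference

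*Protocol*

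**What the plan says.** Protocol section 13.1 makes two power statements, both at alpha 0.05.

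- **Whole trial (Cohort A).** The study is "powered to detect approximately an overall 13% difference between treatment and placebo groups in a repeated measures mixed model analysis", and "A total of 90 subjects will provide 90% power to detect this difference at a significance level (alpha) of 0.05". Allocation is 2:1, so 90 subjects means 60 active and 30 placebo.
- **Adolescents (Cohort B).** For an assumed overall difference of 20%, "a minimum of 18 adolescents aged 12- <18 (Approximately 12 active and 6 placebo) would provide 80% power to detect a difference". The stated purpose is "providing an initial estimate of efficacy and a description of safety in this population".

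Section 5.1 limits the adolescent group, "with a minimum of 18 and a maximum of 24 subjects aged 12 and <18 years of age". Section 13.3.3 specifies a two-sided test from a "repeated measures mixed model of the log-transformed 4-hour C-peptide AUC response at 12, 16 and 24 weeks". No SD is given for either calculation. Section 13.1 also says that Cohorts B and C will be analysed separately as well as combined. The synopsis repeats the 90-subject statement but gives no power for Cohort B.

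**The concern.** Going from 60 v 30 to 12 v 6 cuts the sample fivefold, while the target difference rises only from about 13% to 20%. An increase of about half in the effect does not pay for a fivefold loss of sample, even with the power lowered from 90% to 80%. The adolescent figure therefore looks too high beside the main one.

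The 80% is the power printed for the minimum adolescent enrolment, and the protocol commits to a separate Cohort B analysis. A reader who believes it would treat a non-significant adolescent result as fair evidence against a 20% effect. If the real power is nearer 55–60%, that reading is unsafe.

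**Working it through.** **Inputs.** From 13.1: 90 subjects, 2:1, 90% power, about 13%; 18 adolescents as 12 v 6, 80% power, 20%; alpha 0.05 for both. From 13.3.3: two-sided test. The SD is not stated, so it is solved from the 90-subject claim. The 90% itself therefore cannot be checked independently. Because 13.1 does not fix the scale of its percentages, three are used: the raw percentage x, ln(1+x) and −ln(1−x).

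**Step 1. Standardised effect each claim needs.** Normal formula: d = (z for 1−α/2 + z for power) × √(1/n₁ + 1/n₂).

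- 60 v 30, 90%: (1.960 + 1.282) × √(1/60 + 1/30) = 3.242 × 0.2236 = 0.725; noncentral t, 0.733.
- 12 v 6, 80%: (1.960 + 0.842) × √(1/12 + 1/6) = 2.802 × 0.5 = 1.401; noncentral t, 1.492.
- Ratio: 1.401/0.725 = 1.93 (normal); 1.492/0.733 = 2.04 (t).

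**Step 2. Ratio of the stated differences.** Raw: 0.20/0.13 = 1.54. Upward log: 0.182/0.122 = 1.49. Downward log: 0.223/0.139 = 1.60. All fall short of 1.93, so one SD cannot serve both claims.

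**Step 3. Power of 12 v 6 at the implied SD.** On the raw scale the SD is 0.13/0.733 = 0.177 (t) or 0.13/0.725 = 0.179 (normal). By the normal formula the power is Φ(0.20/(0.179 × 0.5) − 1.960) = Φ(0.27) = 61%; the noncentral t on 16 df gives 56%.

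| | Raw | Upward log | Downward log |
|---|---|---|---|
| Implied SD (t) | 0.177 | 0.167 | 0.190 |
| Power, 12 v 6, t | 56% | 54% | 60% |
| Power, 12 v 6, normal | 61% | 58% | 64% |
| Power, 16 v 8 (maximum of 24), t | 70% | 67% | 74% |
| Power, 16 v 8, normal | 73% | 70% | 76% |
| Difference detectable with 80%, 12 v 6, t | 26.5% | 28.3% | 24.7% |
| Adolescents needed at 2:1 for 80%, t | 30 | 33 | 30 |
| SD needed for 80% at 12 v 6, t | 0.134 | 0.122 | 0.150 |
| That SD ÷ implied SD, t | 0.76 | 0.73 | 0.79 |
| That SD ÷ implied SD, normal | 0.80 | 0.77 | 0.83 |

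All power figures in the table are for a 20% difference. The 80% is not reproduced in any column.

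**Step 4. Sensitivity.** Reading 13% as rounded from anything between 12.5% and 13.5% widens the 12 v 6 range to 51–68% over both methods. The final-analysis alpha of 0.0498 changes almost nothing. Losing two error df to covariates (14 df) gives 53–59%. One-sided testing in both calculations gives 59–67%; for the adolescents only, 67–75%.

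**Step 5. Reverse check.** With the raw-scale SD of 0.134 that makes the adolescent 80% true, 60 v 30 would have about 99% power for 13%, not 90%.

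**Step 6. Precision.** The expected 95% CI half-width at 12 v 6 is 2.120 × SD × 0.5 = 0.188 (raw), 0.177 (upward log) or 0.201 (downward log). That is about the size of the assumed effect (0.20, 0.182 and 0.223).

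**The case against.** The strongest reply is that this is conditional. The protocol states no SD, and the one used here comes from a mixed group aged 12 to under 41 with up to five years of disease. If adolescents vary less, by about 17–27%, both statements can be true. That stands as logic, but 13.1 neither states nor suggests it. Its adolescent argument (faster C-peptide decline, an equal or larger treatment effect) concerns the size of the difference, which is already set at 20%.

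A second reply is that the adolescent sentence names no scale or sidedness. Mixing scales, with 13% as ln 1.13 and 20% as −ln 0.80, gives 71% (t) or 75% (normal); the opposite mix gives 44% (t). So the uncertainty is wider than the same-scale range, but reaching 80% takes a contrived combination, such as mixed scales together with a one-sided test for the adolescents only.

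Repeated measures and covariate adjustment do not help. The 90-subject claim rests on the same model, so any gain is already in the implied SD. The phase 2a contrast in section 1.1 (+19.5% v −8.8%, or 28.3 points) would give 84–88% power, but 13.1 assumes 20%.

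Finally, Cohort B is a secondary subgroup described as giving an initial estimate. That limits the consequence; it does not make the printed figure right.

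**Conclusion.** The concern holds. On a common SD, a common effect scale and a two-sided 0.05 test, 12 v 6 has 54–60% power for a 20% difference by the noncentral t, the suitable method at this size, or 58–64% by the normal approximation. A true 20% effect would be missed in 40–46% of trials by the t calculation, not 20%. Even 24 adolescents do not reach 80% for that difference. It is firm that the power is well below 80% under these assumptions; the exact value depends on an SD the protocol does not give. The 18 also carry no stated drop-out allowance, whereas the 90 are raised to 99, so the comparison is if anything generous. The primary analysis and total sample size are unaffected. The statement should be corrected.

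**What to change.** Change one sentence in section 13.1, in one of these ways:

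- state the adolescent SD, effect scale and method, justify an SD about 17–27% below the one implied for the whole trial, and keep 80%; or
- give the power of 12 v 6 for a 20% difference as roughly 55–60%; or
- say that 12 v 6 detects a difference of about 25–28% with 80% power.

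In each case, present the Cohort B result as an estimate with a 95% confidence interval, which matches the purpose the section already gives. Printing the SD behind the 90-subject figure as well would let a reader check both.

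The cost is a less favourable stated power for the adolescent subgroup. Enrolment limits, the primary analysis and the synopsis need no change.
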